# **REVISION HISTORY**

| Revision | Version Date | Summary of Changes   | Consent |
|----------|--------------|--|---------|
| #        |              |  | Change? |
| 2        |              | Responses to SRC questions                                       |         |
| 3        | 2-2-2021     | Responses to IRB   | yes     |
| 4        | 7-21-2021    | Remove the presence of breast implants as an exclusion criterion | No      |
|          |              |  |         |
|          |              |  |         |

# 1.0 Study Summary

| Study Title
Study Design
Study Specific
Abbreviations/
Definitions | Added value of contrast enhanced mammography for breast
cancer staging in patients referred for a second opinion to a
tertiary cancer center
Prospective observational cross-sectional or correlational
study
CEM: contrast enhanced mammography
BC: breast cancer
OSF: outside facility (medical institution or office outside of
MD Anderson)
FFDM: full field digital mammogram (2D mammogram)
LE: low energy images (a part of CEM exam, FFDM
equivalent)
DBT: digital breast tomosynthesis (3D mammogram)
US: ultrasound   |
|--|--|
| Primary Objective
Secondary
Objective(s)                                 | 
 
To compare the accuracy of CEM and LE images (equivalent of FFDM as the standard of care) for the detection of additional cancer sites in the affected breast and in the contralateral breast. For the purpose of the study, up to 4 additional biopsy sites will be included in the analysis.
 
1. To evaluate the sensitivity, specificity, positive and negative predictive value of CEM compared to LE CEM images (FFDM equivalent), DBT and ultrasound for the detection of additional malignant lesions in the ipsilateral and contralateral breast.
 
2. To evaluate the difference of the index cancer size estimation among CEM, LE images, DBT, and ultrasound compared to pathology measurements as the ground truth.
 
3. To evaluate the incremental cancer detection rate provided by CEM, DBT, and US compared to the OSF diagnosis.
 
 |
| Exploratory
Objective(s)  | 
 
To evaluate the rate of referral to breast MRI in the study cohort.
 
To evaluate the performance of MRI for breast cancer diagnosis and compare it with other imaging modalities of CEM, LE images, DBT and ultrasound.
 
To evaluate the feasibility of CEM-guided biopsy of CEM- only detected lesions. The technical success of CEM guided biopsies will be determined by the
 
  |

|  | fraction of biopsies that achieve adequate sampling of the target.  |  |  |
|--|---|--|--|
| Research
Intervention(s)/
Investigational
Agent(s)
IND/IDE # | IV injection of iodinated contrast material   |  |  |
| Study Population   | 
 
Female patients with known invasive or in-situ breast cancer diagnosed at an outside facility and presenting to MD Anderson for staging with imaging.
 
Female patients referred from outside institutions with imaging findings categorized as highly suspicious (BI-RADS 5 or 4C) on outside imaging or on re-review by MD Anderson's radiologists, and referred for staging at MDACC.
 
 |  |  |
| Sample Size  | 83  |  |  |
| Study Duration for
individual
participants                         | One diagnostic CEM imaging examination
In addition, if indicated, one CEM-guided biopsy  |  |  |

# 2.0 Objectives\*

- 2.1 Primary Objectives
  - To compare the accuracy of CEM and LE images (equivalent of FFDM as the standard of care) for the detection of additional cancer sites in the affected breast and in the contralateral breast.

## 2.2 Secondary Objectives

- To evaluate the sensitivity, specificity, positive and negative predictive value of CEM compared to LE CEM images (FFDM equivalent), DBT and ultrasound for the detection of additional malignant lesions in the ipsilateral and contralateral breast.
- To evaluate the difference of the index cancer size estimation among CEM, LE images, DBT, and ultrasound compared to pathology measurements as the ground truth.
- To evaluate the incremental cancer detection rate provided by CEM, DBT, and US compared to the OSF diagnosis.
- 2.3 Exploratory Objectives
  - To evaluate the rate of referral to breast MRI in the study cohort.
  - To evaluate the performance of MRI for breast cancer diagnosis and compare it with other imaging modalities of CEM, LE images, DBT and ultrasound.
  - To evaluate the feasibility of CEM-guided biopsy of CEMonly detected lesions. The technical success of CEM guided biopsies will be determined by the fraction of biopsies that achieve adequate sampling of the target.

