# 3.0 Background\*

3.1 *Current MDACC practice protocols* 

As a major tertiary cancer center, MD Anderson Cancer Center has a significant population of patients who present for staging of known breast

cancer (BC) which was already diagnosed at an outside facility (OSF), or who have OSF imaging findings that are assigned category 5 (highly suspicious with the probability of malignancy >95%) or 4C (suspicious with the probability of malignancy 50-95%) according to the American College of Radiology (ACR) Breast Imaging Reporting and Database System (BI-RADS) on OSF imaging [1]. Precise delineation of the extent of disease in the affected breast and evaluation of the contralateral breast are crucial for surgical treatment planning in BC patients [2]. Even in patients with no known BC, a second opinion at a specialized cancer center can make a significant impact on clinical management, changing the original interpretation in 36-47% of lesions [3, 4]. In patients who present with known BC at MDACC, the rate of upstaging upon second opinion interpretation and possible re-imaging is 25%, which changes surgical management in 12% of patients [5]. At the same time, the reoperation rate after breast conservation surgery in BC patients is 19% [5]. This is suboptimal and may be due to underestimation of tumor size, but this rate is lower than the national rate, which reaches 30% [2].

The current protocol for staging of OSF BC cases consists of a second read of interpretable OSF mammograms or repeating technically suboptimal mammograms, followed by ultrasound, ultrasound-guided and/or stereotactic-guided biopsies, when indicated. Some patients also require breast MRI with second look ultrasound and ultrasound- or MRIguided biopsies, which prolongs work-up and delays treatment.

At our institution, using ultrasound and MRI almost doubles the number of additional suspicious breast lesions found on mammography. 45% of these additional lesions are malignant. The sensitivities of mammography (MG), US, and MRI are 36, 71, and 85%, respectively, and their specificities are respectively 76, 68, and 39%, making MRI the most sensitive, and the MG the most specific modality. 18% of additional malignant lesions at MDA are found on MRI only [6]. Unfortunately, the need for breast MRI often delays treatment due to the limited availability of magnet time. MRI is also an expensive imaging test, further limiting access.

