# 4.0 Study Endpoints\*

4.1 Primary study endpoint:

Accuracy of CEM for incremental cancer detection in the ipsilateral and contralateral breasts. For the purpose of the study, up to 4 additional biopsy sites will be included in the analysis.

[figure not shown]
- 4.2 Secondary study endpoints:
  - Sensitivity, specificity, positive and negative predictive value of CEM, LE images, DBT, and ultrasound compared to pathology measurements as the ground truth.
  - The difference of the largest measurement of the index cancer on *LE*, *CEM*, *DBT* and *US* compared to pathology.
  - Incremental cancer detection rate provided by CEM, DBT and US.
- 4.3 Exploratory Endpoints:
  - *Rate of breast MRI utilization and the corresponding diagnosis in the study cohort.*
  - *The fraction of CEM biopsies that achieve adequate sampling of the target.*

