## 5.8 Multiple reader study design

Low-energy images produced as a part of CEM are of sufficient quality for clinical interpretation (equivalent to directly acquired 2D mammographic images), and will be interpreted accordingly by radiologists.

The reader study will have 2 components:

1. The first interpretation of the entire CEM study, including all its components, will be done clinically by one radiologist after the exam is performed. Its results will be actionable and will affect the patient's management.

2. Multiple reader study. The results of this study will not be used for clinical care, and will not be reported to the patients or referring clinicians.

Each patient's study will contain LE images (FFDM equivalent), DBT images, and CEM subtraction images. All these components will be separated and presented to radiologists in different combinations for within-subject comparison. As a part of the multi-reader component, the study images for every patient will be reviewed in 4 sets by 5 radiologists each. Images for the same patients will be read by radiologists with an interval of at least 2 month to prevent case memorization.

1. LE (FFDM equivalent) images only

2. LE (FFDM equivalent) with DBT

3. LE followed by DBT followed by CEM subtraction images

4. LE followed by subtraction images (complete CEM study)

The study radiologists will be aware of the patients' inclusion criteria, but will be blinded to the clinical diagnostic reports, any and all comparison images of any modality outside of the assigned protocol, and the pathology report.

5.9 The sequence of the imaging studies and the parameters to be collected are presented below. The reporting will be done using ACR BI-RADS Fifth edition recommendations.

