## 15.0 Data Management\* and Confidentiality

### 15.1 Statistical considerations

The primary objective of this study is to compare the accuracy of CEM and LE images (FFDM equivalent) for the detection of additional cancer sites in the affected breast and in the contralateral breast among patients with known BC diagnosed or highly suspicious at an outside facility and presenting to MD Anderson for staging imaging. The images of CEM/LE and DBT for each patient will be read/reviewed by 5 radiologists, and the majority agreement among 5 radiologists on the lexicon and BI-RADS assessment will be used for consensus. If all 5 radiologists disagree, then a consensus conference will be held. Pathology results will be considered the ground truth. Breast tissue lesions will be categorized as positive if determined as invasive cancer or DCIS, and otherwise will be categorized as negative that includes the lesions of uncertain malignant potential without subsequent surgical upgrade to invasive cancer or DCIS.

The primary outcome of this study is accuracy determined by comparing the CEM/LE results to that of the pathologic evaluations. Specifically, it is defined as the number of concordant cases between CEM/LE and pathologic evaluation divided by the total sample size. Secondary outcomes include sensitivity, specificity, negative predictive value (NPV) and positive predictive value (PPV). Sensitivity (specificity) is defined as the number of correctly diagnosed positive (negative) cases divided by the total number of confirmed positive (negative) cases, NPV is defined as the number of true negative lesions obtained from CEM/LE divided by the corresponding total predicted number of negative lesions. The PPV is similarly defined for positive breast lesions. Cancer detection rate is defined as number of invasive malignancy or DCIS divided by the total sample size.

A successful CEM guided biopsy is defined as a biopsy which successfully sampled the abnormality in question. This procedure will be considered feasible if 95% patients or more have successful CEM guided biopsy among those who will undergo this procedure, which is similar to the success rate of the prone stereotactic vacuum assisted biopsies [41].

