### 15.3 Statistical analysis plan

Descriptive statistics will be used to summarize clinical variables of interest. Specifically, categorical measures will be summarized using frequencies and percentages and continuous measures will be summarized using means, standard deviations, medians, and ranges. Outcome variables of cancer detection rate, accuracy, sensitivity, specificity, PPV, and NPV will be estimated along with 95% confidence intervals; and compared between the modalities using the McNemar test or the weighted generalized score statistic proposed by Kosinski [38], if deemed appropriate . To account for multiple lesions, outcome variables will be analyzed using generalized liner mix models or extended McNemar's test [39-41], and additional analyses may be further performed if deemed appropriate.

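### Secondary objective 3 measures increments over the outside diagnosis without the in-house LE read, so it cannot separate contrast from new reading and new imaging

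*Combined protocol and SAP*

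**What the plan says.** Section 2.2 states the third secondary objective as "To evaluate the incremental cancer detection rate provided by CEM, DBT, and US compared to the OSF diagnosis". The matching endpoint in 4.2 is "Incremental cancer detection rate provided by CEM, DBT and US"; it names no comparator. LE appears in neither, although the other two secondary objectives both name it.

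Section 15.1 gives the only definition of the rate: "Cancer detection rate is defined as number of invasive malignancy or DCIS divided by the total sample size". It does not define an increment. Section 15.3 says "Outcome variables of cancer detection rate, accuracy, sensitivity, specificity, PPV, and NPV will be estimated along with 95% confidence intervals" and that these outcomes will be compared between modalities; neither LE nor the OSF diagnosis is named in that sentence.

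Section 5.8 plans four reader sets, each read by five radiologists. Set 1 is "1. LE (FFDM equivalent) images only", set 2 is LE with DBT, set 3 is LE, then DBT, then subtraction images, and set 4 is LE followed by subtraction images, described as the complete CEM study.

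On second opinion without CEM, section 3.1 reports that for patients with known cancer "the rate of upstaging upon second opinion interpretation and possible re-imaging is 25" percent. For patients with no known cancer, it describes second opinion as "changing the original interpretation in 36-47% of lesions".

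**The concern.** The objective asks what each modality provides, but its baseline differs from the study reads in more than modality. The OSF diagnosis comes from other readers, other images and an earlier date. The complete CEM study is newly acquired, read in-house, and includes a full mammogram. A cancer missed outside but visible on the new LE images, and still called positive on the complete study, counts towards CEM's increment even if the subtraction images contribute nothing.

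The population makes this a practical matter. All participants are referred from outside for staging, and the protocol's own background says that second opinion with possible re-imaging changes findings in such patients before CEM is used. A reported increment for CEM over OSF could be read as the yield of contrast when it is the yield of referral, re-imaging and contrast together. The DBT and US increments share the problem, with the modality itself in place of contrast.

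**Working it through.** The plan states no figure for objective 3. The 83 patients in section 15.2 are sized for the primary CEM-versus-LE accuracy comparison, and nothing below depends on that calculation.

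**Step 1. Where LE serves as a comparator.**

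- Primary objective (2.1): CEM against LE, for accuracy.
- Secondary objective 1 (2.2): CEM against LE, DBT and US, for sensitivity, specificity and predictive values.
- Secondary objective 2 (2.2): LE is one of the modalities compared with pathology, for index cancer size.
- Secondary objective 3 (2.2) and its endpoint (4.2): LE absent.
- Sections 15.1 and 15.3: no increment defined, and no LE or OSF contrast named for the detection rate.

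**Step 2. What CEM over OSF contains.** Let s(OSF), s(LE) and s(CEM) be the proportions of the same set of additional cancers found by each. Then

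s(CEM) − s(OSF) = [s(LE) − s(OSF)] + [s(CEM) − s(LE)].

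The first bracket is new readers plus new acquisition. The second is what the subtraction images add. Objective 3 reports only the sum. Detection rates per total sample multiply every term by the same factor (additional cancers divided by sample size), so the share held by the first bracket is the same on either scale:

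LE share = [s(LE) − s(OSF)] / [s(CEM) − s(OSF)].

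**Step 3. Possible size.** One input is in the documents. Section 3.1 says "The sensitivities of mammography (MG), US, and MRI are 36, 71, and 85%, respectively", so s(LE) is set at 36%, using the protocol's statement that LE is equivalent to a standard 2D mammogram. The other two inputs are assumptions that the documents do not supply: s(CEM) from 60% to 85%, and s(OSF) of 0%, 18% (half of 36%) or 36%.

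| Assumed CEM | Assumed OSF | CEM − OSF | LE − OSF | CEM − LE | LE share |
|---|---|---|---|---|---|
| 60% | 0% | 60 | 36 | 24 | 36/60 = 60% |
| 60% | 18% | 42 | 18 | 24 | 18/42 = 43% |
| 60% | 36% | 24 | 0 | 24 | 0% |
| 70% | 0% | 70 | 36 | 34 | 36/70 = 51% |
| 70% | 18% | 52 | 18 | 34 | 18/52 = 35% |
| 70% | 36% | 34 | 0 | 34 | 0% |
| 85% | 0% | 85 | 36 | 49 | 36/85 = 42% |
| 85% | 18% | 67 | 18 | 49 | 18/67 = 27% |
| 85% | 36% | 49 | 0 | 49 | 0% |

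Differences are in percentage points. With CEM at 60%, the contrast contribution is 24 points in every row, while the increment over OSF runs from 24 to 60 points according to how well the outside facility did. The endpoint as written could not show which row applies.

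**The case against.** The strongest reply is that the trial already answers the attribution question. The primary objective compares CEM with LE within the same patients, and secondary objective 1 repeats that comparison for sensitivity, specificity and predictive values. This stands. A reader might infer from objective 3 that the trial cannot separate contrast from re-reading; the documents do not support that.

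Second, objective 3 openly names the OSF diagnosis as its baseline, and the total gain over the referral diagnosis is a fair question in women referred for a second opinion. This also stands. The comparator is legitimate for a total effect; what it cannot support is the claim that the increment is provided by CEM.

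Third, DBT and US are measured from the same baseline, so CEM is not singled out. Contrasts among the three are therefore less affected than each increment over OSF, but each increment stays a mixture.

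Fourth, section 15.3 allows comparison of detection rates between modalities, which could include LE. That permits the analysis without specifying it.

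Fifth, set 1 would not isolate a pure referral effect. Its readers are blinded to clinical reports and to comparison images, unlike the second read of outside mammograms described in 3.1. US is excluded from the reader study and taken from medical records (5.3), and the plan does not say whether objective 3 uses the reader-study results or the clinical read. These limits are correct, and the fix has to respect them.

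**Conclusion.** The point holds as a limited one. As written, objective 3 and its endpoint cannot distinguish what contrast adds from what new readers and new acquisition add. The main CEM inference is not affected, and the endpoint is unpowered, so this concerns interpretation and not the validity of the trial.

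The size is unknown. Under the assumptions in the table the LE share is 0% to 60%. It is zero if the outside facility found as much as in-house mammography, and it could be negative if blinded LE readers found less than the outside facility did.

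A reader might apply the 25% upstaging rate to all 83 patients and conclude that about 21 women (0.25 × 83 = 20.75) would be wrongly credited to CEM. The documents do not support that. The 25% is upstaging, not additional breast cancers. It refers to patients with known cancer, whereas the cohort also admits BI-RADS 4C and 5 referrals. It includes possible re-imaging and is not split by modality; the title of the cited source shows that whole-breast and regional nodal ultrasound were part of the work-up. The figure shows only that a second-opinion and re-imaging effect exists without CEM.

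**What to change.** 1. Add LE (reader set 1) to objective 3 in 2.2 and to the endpoint in 4.2. Name the OSF diagnosis as comparator in 4.2 too, and define the increment and its denominator in 15.1.
2. From the planned reader sets, report LE over OSF, LE with DBT (set 2) over LE, complete CEM (set 4) over LE, and set 3 over set 2.
3. Attribute to contrast only pathology-proven cancers that are positive on the CEM set and negative on the matching non-contrast set: set 4 against set 1, and set 3 against set 2.
4. Keep CEM, DBT and US over OSF, but label each as the total effect of referral plus that imaging.
5. Describe LE over OSF as the combined effect of new readers and new acquisition, read blinded to prior images, and not as an isolated referral effect. Keep US outside the stepwise reader-set comparison, because it comes from clinical records.

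The cost is a change of wording and one extra tabulation. All four sets are already planned for every patient, so no new patients, exposures or reads are needed. The increment attributed to CEM may turn out smaller.

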## 2.4 Hypothesis

We hypothesize that CEM will improve the diagnostic accuracy of incremental breast cancer detection compared to standard 2D mammography and will improve the accuracy of the index cancer size estimation. The overarching goal is to determine whether CEM will reduce the need for breast MRI and decrease the overall time and cost of preoperative imaging evaluation of patients with breast cancer.

# 3.0 Background\*

3.1 *Current MDACC practice protocols* 

As a major tertiary cancer center, MD Anderson Cancer Center has a significant population of patients who present for staging of known breast

cancer (BC) which was already diagnosed at an outside facility (OSF), or who have OSF imaging findings that are assigned category 5 (highly suspicious with the probability of malignancy >95%) or 4C (suspicious with the probability of malignancy 50-95%) according to the American College of Radiology (ACR) Breast Imaging Reporting and Database System (BI-RADS) on OSF imaging [1]. Precise delineation of the extent of disease in the affected breast and evaluation of the contralateral breast are crucial for surgical treatment planning in BC patients [2]. Even in patients with no known BC, a second opinion at a specialized cancer center can make a significant impact on clinical management, changing the original interpretation in 36-47% of lesions [3, 4]. In patients who present with known BC at MDACC, the rate of upstaging upon second opinion interpretation and possible re-imaging is 25%, which changes surgical management in 12% of patients [5]. At the same time, the reoperation rate after breast conservation surgery in BC patients is 19% [5]. This is suboptimal and may be due to underestimation of tumor size, but this rate is lower than the national rate, which reaches 30% [2].

The current protocol for staging of OSF BC cases consists of a second read of interpretable OSF mammograms or repeating technically suboptimal mammograms, followed by ultrasound, ultrasound-guided and/or stereotactic-guided biopsies, when indicated. Some patients also require breast MRI with second look ultrasound and ultrasound- or MRIguided biopsies, which prolongs work-up and delays treatment.

At our institution, using ultrasound and MRI almost doubles the number of additional suspicious breast lesions found on mammography. 45% of these additional lesions are malignant. The sensitivities of mammography (MG), US, and MRI are 36, 71, and 85%, respectively, and their specificities are respectively 76, 68, and 39%, making MRI the most sensitive, and the MG the most specific modality. 18% of additional malignant lesions at MDA are found on MRI only [6]. Unfortunately, the need for breast MRI often delays treatment due to the limited availability of magnet time. MRI is also an expensive imaging test, further limiting access.

